## 7.4 Handling of Missing, Unused, and Spurious Data and Dropouts

The analysis will be based on all observed data. If appropriate, missing data will be imputed per study specific SAP addendum. Data will be cleaned throughout the study, and there is no plan to exclude spurious data.

## 7.5 Adjustments for Multiple Comparisons

No adjustments for multiple comparisons will be made. If it is needed, details will be provided in study specific SAP addendum.

## 7.6 Demographic and Other Baseline Characteristics

Demographics and baseline characteristics will be summarized at subject level. Baseline is defined as the last measurements prior to surgical or medical procedure. All the variables will be summarized overall and/or by group if applicable.

Summaries of continuous variables will present n, mean, median, 25th and 75th percentiles, SD, minimum and maximum. Summaries of categorical variables will present counts and percentages. Any missing data will be excluded from the corresponding summaries, and number of missing data will be reported.

## 7.6.1 Demographics

Demographic variables include but are not limited to

- Age at enrollment
- Gender
- BMI (kg/m^2)

## 7.6.2 Baseline Characteristics

Baseline characteristics include but are not limited to:

- Medical history
- Reason for surgical or medical procedure

## 7.7 Procedural Characteristics

Procedural characteristics will be summarized if applicable.

## 7.8 Interim Analyses

Interim analysis will be completed as needed.

## 7.9 Evaluation of Objectives

### 7.9.1 Primary Objective

The primary objective is to evaluate the safety and performance of Medtronic market released products for surgical innovations and surgical robotics.

#### 7.9.1.1 Hypothesis

No specified hypotheses for this objective.

#### 7.9.1.2 Endpoint definition

The safety and performance of Medtronic market released surgical products is evaluated by the surgical or medical procedure related and/or the product related event rate. Depending on the follow-up schedule, the time for assessing the event rate varies. For products following the short-term schedule, the event rate is assessed post procedure or within 30 days post-procedure; for products following the long-term schedule, the time point for event rate assessment depends on the products.

In the case report form (CRF), the relatedness is collected as 4 categories: not related, possible, probable, and causal. For the primary endpoint, events classified as, 'possible', 'probable', 'causal' are considered related.

#### 7.9.1.3 Analysis Method

Event rate is calculated as number of events divided by number of units (e.g. subjects or product uses) where events are evaluated among subjects who have enrolled, met all the inclusion/exclusion criteria, and underwent surgical procedure. If there are more than one event per unit, only the first event is relevant to the primary objective.

Two-sided 95% confidence interval (CI) of the event rate will be calculated using Binomial distribution. All the events will be summarized in a table by Medical Dictionary for Regulatory Affairs (MedDRA)

terms. The number of events, and the number and percentage of subjects who experienced the event will be reported. Surgical or medical procedure related events and/or the product related events will be listed.

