6.2. Analysis Requirements

Specific analysis requirements are documented, as applicable, and are integrated with the CIP in one of two ways, either via an associated Analysis Plan (AP) or Addendum (AD). Refer to the decision process provided in (Figure 2).

An AP, at a minimum, specifies the intended sample size estimates, analysis time points, reporting, etc. for a sub-population (and their data) from the overall PSR cohort of a given Condition/Therapy. The AP document can be specific to a patient population, therapy, product or product group and defines how the data will be analyzed. It does not contain any procedures or data collection requirements that differ from the CIP; therefore, an AP has no impact on the patient or how the site conducts PSR activities.

An AD can be specific to a patient population, therapy, product or product group, but unlike the AP, it does contain procedure and/or data collection elements that differ from the CIP. The AD describes the specific procedures that differ from the CIP (e.g., regulatory directed requirement), therefore an AD may impact the patient and/or how the site conducts PSR activities. An AD may have IRB/ Ethics Board, consent and potentially regulatory implications; therefore, additional site readiness activities may be needed, refer to Section 9.2. An AD includes, but is not limited to, unique procedure requirements, objectives/endpoints, statistical methodology, analysis cohort, and reporting timelines.

Figure 2: Decision tree for use of AP or AD

*Extensible Design: Supports Multiple Analysis Plans and/or Addendums

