Regulatory reporting of Adverse Events will be completed according to local and national law and regulatory requirements. Refer to Table 3 and Table 4 for a list of required site and Medtronic reporting requirements. It is the responsibility of the site to comply with the Adverse Event reporting requirements of their Ethics Board.

All sites are required to follow their local regulatory reporting requirements for market-released products.

Device deficiencies information will be collected throughout the registry and be reported to Medtronic upon site's first awareness. Specific event reporting requirements may be outlined for a given condition, procedure and/or therapy in the Condition/Therapy Appendix.

13. Data Review Committees

A Clinical Event Committee (CEC) may conduct a review of reported events and deaths at regular time intervals, if applicable. The need for CEC review will be determined by Condition/Therapy and the end use of the data (e.g., regulatory reporting, publications, etc.). Use of a CEC will be documented in the associated AP or AD. The CEC is a committee comprised of independent experts with applicable technical and clinical backgrounds.

The committee will be provided with the reporting clinician's assessment of the event and actions taken. The committee is responsible for reviewing the clinician's assessment and adjudicating the event as applicable. If the CEC disagrees with the clinician's assessment, the rationale will be provided to the clinician. Both determinations are retained. The CEC determination will be used for analysis purposes.

14. Statistical Design and Methods

The purpose of the PSR is to better characterize the safety and/or performance of market-released products, therefore sample size calculations serve to ensure sufficient precision for characterization of performance. The exact definition of sufficient precision will vary based on the intended end use of the data and product type. The general concept is that sample sizes should be large enough to generate meaningfully narrow confidence intervals for population parameters of interest. Specific analysis requirements, statistical methods including required effective sample size determinations are defined in the PSR associated AP or AD; refer to Section 6.2.

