## 3. Introduction

In 2011, Medtronic launched the global Product Surveillance Registry (PSR). It was built on more than 25 years of post-market clinical surveillance experience and designed to provide continuing evaluation and periodic reporting of safety and effectiveness of market-released products for their intended use.

Data collected in the PSR supports post-market surveillance activities and post-approval studies initiated by Medtronic, regulated by local governments, or conducted to fulfill government and/or regulatory

authority requests. The PSR also obtains clinical evidence to guide the development and improvement of medical devices, therapies, device guidelines, patient services/solutions and provide clinical data to support health economics and clinical outcomes research.

The PSR supports multiple Medtronic Surgical Innovations (SI) and Surgical Robotics (SR) products used in a wide range of surgical and medical procedures including minimally invasive procedures, robotic procedures, endoscopic procedures, and percutaneous procedures.

This Statistical Analysis Plan (SAP) is designed to document, before data is analyzed, the planned statistical analyses, and to support regulatory reports and *ad hoc* data requests. Reports generated using the PSR data may not contain all the objectives described below; however, if a report contains an objective outlined within this document, the analysis of that objective will be performed as described in this SAP. If additional analyses are required but not covered in this SAP, a study specific SAP addendum may be developed. A thorough explanation and rationale for any analyses conducted differently than outlined in the PSR Surgical Platform Base Clinical Investigation Plan (CIP) or SAP will be provided in conjunction with the analyses/output.

The following document was used to create this SAP: Product Surveillance Registry Platform Base Clinical Investigation Plan, Version 9, 19 May 2020 and its Surgical Appendix, Version 2, 07 Dec 2020.

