### 4.1 Primary Objective

The primary objective is to evaluate the safety and performance of Medtronic market released products for surgical innovations and surgical robotics. The objectives include, but are not limit to the following:

- To estimate the surgical or medical procedure related and/or the product related event rate
- To characterize the surgical or medical procedure related events and/or the product related events

Depending on the products, the primary endpoint may be assessed at different time point, e.g. after procedure, 30-day post procedure, or 5 years post procedure. For details, please refer to the study protocol.

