#### 7.1.3 Analysis Sets

Subjects included in any analysis sets must consent to the PSR, unless a full waiver of consent has been approved by the site's IRB or EC, and meet all the inclusion/exclusion criteria. They must have been treated with at least one Medtronic market released surgical product. Additional inclusion/exclusion criteria include, but are not limited to specific components or models, time frame, data cutoff date and geography. For details, please refer to Analysis Plan (AP) or Addendum (AD).

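### The SAP's default primary event rate has no follow-up condition or censoring rule, so at long-term time points incomplete follow-up biases it low

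*SAP*

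**What the plan says.** SAP 7.9.1.3 defines the primary estimator once, for every follow-up schedule: "Event rate is calculated as number of events divided by number of units (e.g. subjects or product uses) where events are evaluated among subjects" who enrolled, were eligible and had the procedure. Only the first event per unit counts, and the 95% interval is binomial.

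The same rate is meant for long follow-up. SAP 4.1 lists possible primary time points that include "30-day post procedure, or 5 years post procedure", and SAP 7.9.1.2 states that "for products following the long-term schedule, the time point for event rate assessment depends on the products". Surgical Appendix B.4 allows follow-up to 60 months.

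On incomplete follow-up, SAP 7.4 says "The analysis will be based on all observed data" and leaves any imputation to a study-specific addendum. SAP 7.1.3 leaves further restrictions such as "specific components or models, time frame, data cutoff date and geography" to the Analysis Plan (AP) or Addendum (AD). Kaplan-Meier with log-log limits appears in SAP 7.9.2, but for survival outcomes under the secondary objective. SAP 4.2 makes those long-term survival analyses optional.

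The formula is a default with some force. SAP Section 3 says that "if a report contains an objective outlined within this document, the analysis of that objective will be performed as described in this SAP", although it also permits a different analysis if this is explained and justified.

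**The concern.** A proportion of all treated units is a sound estimate of risk at a time point only if nearly every unit is observed to that time or to an event. That is plausible at 30 days and much less certain at 5 years. The plan itself foresees losses. SAP 6.2 names attrition, and Protocol 10.12 lists withdrawal, loss to follow-up, site closure and inactive products as reasons for exit. SAP 7.8 allows interim analyses as needed, so a rate could also be reported before all subjects reach the time point.

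Under the written formula these subjects stay in the denominator as if they had been seen to be event-free. The error goes one way: the reported rate of procedure- or product-related events is too low. In safety surveillance this is the less welcome direction, and the binomial interval gives no sign of it.

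**Working it through.** **Inputs from the SAP.** Estimator and binomial interval: 7.9.1.3. Time point of 5 years: 4.1. Event rates of 5% to 20% and their sample sizes: 6.1.

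**The plan's own figure.** The formula in SAP 6.1 gives N = 1.96² × 0.20 × 0.80 / 0.05² = 245.86, rounded up to 246, as tabulated. The other eight cells reproduce as well.

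**Assumptions, because the documents give neither attrition nor event timing.** Dropout is independent of events at d = 2%, 5% or 10% per year, which means 9.6%, 22.6% or 41.0% lost by 5 years. The event hazard is constant.

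**Expected value of the written estimator.** With true risk R at time T:
- λ = −ln(1 − R)/T and μ = −ln(1 − d)
- expected rate p = λ/(λ + μ) × [1 − exp(−T(λ + μ))]

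For R = 0.20, T = 5 and d = 0.05: λ = 0.0446, μ = 0.0513, and p = 0.4653 × (1 − 0.6190) = 0.177.

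Coverage is the probability that the exact (Clopper-Pearson) interval from x ~ Bin(246, p) contains 20%, found by enumeration. Without dropout it is 96%.

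| Yearly dropout | Expected rate (true 20%) | Bias, points | Coverage |
|---|---|---|---|
| 2% | 19.1% | −0.9 | 95% |
| 5% | 17.7% | −2.3 | 88% |
| 10% | 15.7% | −4.3 | 64% |

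**How far this depends on the case chosen.**
- *Other cells of the SAP table.* 20% with N = 246 is the most sensitive cell. At 5% yearly dropout the other eight keep coverage of 92% to 97%. The relative bias is similar, but smaller samples have wider intervals.
- *Shorter time point.* With a 20% risk at 1 year and 5% yearly dropout, λ = 0.2231 and p = 0.195, a bias of about 0.5 points.
- *Early events.* If 80% of the events (e = 0.16) occur before any dropout, the remaining hazard is λ = −ln(1 − 0.04/0.84)/5 = 0.00976, and p = e + (1 − e) × λ/(λ + μ) × [1 − exp(−T(λ + μ))]. The rates become 19.8%, 19.5% and 19.1%, with coverage of 96%, 96% and 95%.
- *Time point not yet reached.* Suppose 3-year uniform accrual, a cutoff 6 years after first enrollment, no dropout and constant hazard. The mean of 1 − exp(−λ min(f, 5)) over f uniform on 3 to 6 years is 17.5%, with 87% coverage. This applies only if a study reports a 5-year rate that early.

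**Alternative.** In simulations with N = 246, true risk 20%, constant hazard and 5% or 10% yearly dropout, 1 minus Kaplan-Meier at 5 years averages 20.0%, and its log-log interval covers in about 95% of samples.

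**The case against.** The strongest reply is that this is a platform SAP and leaves detail to each study by design. Protocol Section 14 says "Specific analysis requirements, statistical methods including required effective sample size determinations are defined in the PSR associated AP or AD", and Protocol 6.2 says "An AP, at a minimum, specifies the intended sample size estimates, analysis time points, reporting, etc. for a sub-population". An AP, AD or SAP addendum may well define an evaluable set or a censoring rule. This stands as a limit: the point concerns the default, and nobody can infer from these documents that any actual long-term study lacks a rule. It does not remove the point. The objective is covered by this SAP, Section 3 makes the SAP's method the starting position, and no passage asks the study documents to add a follow-up rule for this rate.

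A second reply is that loss may be small. Surgical Appendix B.4 requires a status assessment whether or not the patient is seen, and B.6 allows medical record review. Both will limit loss without excluding it. At 2% per year the bias is under 1 point.

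A stronger reading is also tempting: that SAP 7.4 could mean a completer denominator, that this would bias the rate high, and that the result therefore swings between two unstated choices. The documents do not support this. SAP 7.9.1.3 names the treated population, and using all observed data defines no completer set. Nor is a completer analysis biased high in general. A strict completer set is unbiased under independent dropout, and is biased low if events trigger exit. The upward bias needs a hybrid that keeps events from dropouts and removes event-free dropouts, and the plan does not describe one.

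**Conclusion.** The point holds for the default primary event rate at long-term time points. The written formula has no follow-up condition or censoring rule and understates the risk when follow-up is incomplete. The size to quote is the bias of the written rule: 2.3 points at 5% yearly dropout for a true 5-year risk of 20%, a little under half of the 5-point half-width that N = 246 is meant to deliver, and 4.3 points at 10%.

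These figures rest on assumed independent dropout and constant hazard, and on the most sensitive cell of the SAP table. The effect is minor at 1 year, at low dropout, with mostly early events, and at 5% yearly dropout in most of the other cells. The change is worth making before any long-term rate is reported, because the needed method is already in the SAP.

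**What to change.** In SAP 7.9.1.3, for long-term primary time points only:

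- Estimate the cumulative risk of the first related event per subject at the stated time by 1 minus Kaplan-Meier, with the log-log 95% interval of SAP 7.9.2. Cumulative incidence with event-free death as a competing event is an alternative.
- Count events and follow-up time to the same defined date: the last date on which event status is known, or the data cutoff. Events are reported on awareness, while assessments may be only annual. Counting events between assessments but censoring event-free subjects at the previous one would bias the rate high, to about 20.4% and 21.0% for a true 20% at 5% and 10% yearly dropout in a simulation with annual assessments.
- Report the number still at risk at the time point.
- Keep the crude all-treated proportion as a labelled supplement.

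Leave the post-procedure and 30-day rates unchanged.

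**Cost.** This is a change of SAP wording. It needs event dates and last-known-status dates; the CRFs are under separate cover, so whether they collect these could not be checked. The interval becomes wider. At 20% and N = 246 the mean half-width is about 5.4 points against 4.9 for the crude proportion at 5% yearly dropout, and 5.8 against 4.7 at 10%. Keeping a 5-point half-width would take about 283 or 330 subjects instead of 246.

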## 5. Investigation Plan

### 5.1 Study Design

The PSR is designed to conduct active prospective post-market surveillance. Its extensible design allows products to be easily added following market release. Only subjects treated with an eligible product can be enrolled. Data collection is intended to align with routine clinical care practice.

The PSR Platform Base CIP format has a modular design which provides a framework for the collection of surveillance data to support Medtronic's product portfolio. The PSR Platform Base CIP for a given Condition/Therapy is comprised of the following:

- PSR Core: defines elements applicable to all PSR subjects, products, conditions, or therapies
- PSR Condition/Therapy Appendix: expands on the content of the PSR Core to further define specific procedure and data collection requirements for a given Condition/Therapy and is intended to align with routine care practices

PSR Surgical Platform base CIP includes PSR Platform Base CIP and its Surgical Appendix. Specific analysis requirements for each study are documented, as applicable, and are integrated with the CIP in one of two ways, either via an associated Analysis Plan (AP) or Addendum (AD). This SAP intends to cover most common objectives described in the above documents and provides statistical analysis details. In case any of the objectives or specific analysis is not covered, they will be included in SAP addendum.

Together, this SAP and its SAP addendum comprise the study-specific SAP.

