## 7.11 Changes to Planned Analysis

Any deviation from the analyses described in the statistical analysis plan and a justification for making the change will be documented in the final report if applicable or relevant study summary.

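### SAP 7.9.1.3 gives product uses the same plain binomial 95% CI as subjects, which is too narrow when a subject contributes several correlated uses

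*SAP*

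**What the plan says.** SAP 7.9.1.3 defines the primary event rate as "number of events divided by number of units (e.g. subjects or product uses"). On repeated events it says: "If there are more than one event per unit, only the first event is relevant to the primary objective". It then states one interval without distinguishing the unit: "Two-sided 95% confidence interval (CI) of the event rate will be calculated using Binomial distribution". It does not say whether the exact or the normal-approximation form is meant.

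Several uses per subject are possible. Section A of the protocol's Surgical Appendix describes procedures done with a single Medtronic product or with several, and SAP 7.1.3 sets a minimum of one product per subject and no maximum. The same section lets a study narrow its analysis set: "Additional inclusion/exclusion criteria include, but are not limited to specific components or models".

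On which document governs, SAP section 3 says that "if a report contains an objective outlined within this document, the analysis of that objective will be performed as described in this SAP". SAP 5.1 sends only uncovered matters elsewhere: "In case any of the objectives or specific analysis is not covered, they will be included in SAP addendum". Protocol section 14 says: "Specific analysis requirements, statistical methods including required effective sample size determinations are defined in the PSR associated AP or AD". SAP 7.11 adds: "Any deviation from the analyses described in the statistical analysis plan and a justification for making the change will be documented".

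**The concern.** Uses in one subject share the patient and usually the operator and the operation, so their outcomes may well be positively correlated. A binomial interval treats each use as independent information. The first-event rule makes each use a yes/no outcome, but it works within a unit and leaves several correlated units from one subject in the denominator.

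The interval is the stated measure of precision for the primary objective, and both protocol section 14 and SAP section 6 base the sample size on precision. An interval that is too narrow makes a safety rate look more certain than it is. Because this is the base SAP of the surgical platform, its default reaches every study that relies on it.

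**Working it through.** **The plan's own figure.** SAP 6.1 uses N = 1.96² × p(1−p) / halfwidth². At p = 20% and half-width 5%: 3.8416 × 0.16 / 0.0025 = 245.86, rounded up to 246, as tabulated. All nine cells of the table reproduce. The formula assumes independent units.

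**Assumed inputs.** The documents give neither m, the number of uses per subject, nor the ICC. The range taken was mainly m = 2, 3, 5 and ICC 0.05 to 0.3. To read the ICC: the risk for another use, given an event in one, is p + ICC × (1−p). At p = 20% this is 20% + 0.1 × 80% = 28% for ICC 0.1, and 36% for ICC 0.2.

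**Loss of information.** The design effect is DE = 1 + (m−1) × ICC. The effective number of units is 246 / DE, and the correct half-width is 5 points × √DE.

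| m | ICC | DE | Effective units | Half-width (points) |
|---|---|---|---|---|
| 2 | 0.1 | 1.1 | 224 | 5.2 |
| 3 | 0.2 | 1.4 | 176 | 5.9 |
| 5 | 0.2 | 1.8 | 137 | 6.7 |

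**Coverage.** Beta-binomial simulation, 40,000 replicates per cell, Monte Carlo error about 0.1 to 0.2 points, with the SAP's interval read as Clopper-Pearson. The adjusted interval is Clopper-Pearson on n / max(1, DE), where DE is estimated as the cluster-robust variance of the rate (ratio estimator, factor k/(k−1) for k subjects) divided by p(1−p)/n. A dash means not listed here.

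At p = 20%, about 246 uses:

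| Uses per subject | ICC | Plain | Adjusted |
|---|---|---|---|
| 1 | none | 96.2% | – |
| 70% of subjects one, 30% two | 0.1 to 0.3 | 96.0% to 94.9% | – |
| 2 | 0.1 | 95.4% | 96.0% |
| 2 | 0.2 | 94.2% | – |
| 3 | 0.05 | 95.3% | – |
| 3 | 0.1 | 94.2% | 95.8% |
| 3 | 0.2 | 91.9% | 95.8% |
| 5 | 0.1 | 91.9% | – |
| 5 | 0.2 | 87.9% | 95.6% |
| 1 to 5, mean 3 (240 uses) | 0.05 | 94.3% | – |
| 1 to 5, mean 3 | 0.1 | 92.8% | – |
| 1 to 5, mean 3 | 0.2 | 89.8% | 95.6% |

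At lower rates, plain interval:

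| p, uses | m=2, ICC 0.2 | m=3, ICC 0.1 | m=3, ICC 0.2 |
|---|---|---|---|
| 10%, 138 | 95.1% | 95.0% | 93.2% |
| 5%, 72 | 94.6% | 94.8% | 92.8% |

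The exact interval is conservative, which absorbs weak clustering. The normal-approximation form has no such reserve: in a separate run of 50,000 replicates at p = 10% and about 140 uses, it covered 93.3% with independent units and 92.3% at m = 2, ICC 0.1, against 96.8% and 95.8% for the exact form.

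**Opposite case.** If at most one use per subject can carry the event (m = 2 or 3), the plain interval covers too often, 97.4% to 99.7%.

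**The case against.** The strongest reply is that the trigger is hypothetical. Three things must hold together: product uses as the unit, several uses per subject in one denominator, and positive correlation. Product uses appear only as an example, and restricting an analysis to one component or model may leave one use per subject. This stands, and it makes the point conditional.

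Second, study-level methods belong in the analysis plan (AP), addendum (AD) or SAP addendum, which are not among the documents reviewed. A study could indeed correct the interval there, or depart from the SAP with a documented reason. But nothing requires it. This interval is already covered by the base SAP, so section 3 makes the plain binomial form the default, and 5.1 refers only uncovered matters onward.

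Third, the direction of the error depends on how an event is attributed to a use, which neither document says. Procedure-related events belong to the procedure, and if each could be assigned to only one use per subject, the plain interval would be conservative. This also stands, and it means the attribution rule should be stated.

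Fourth, the largest losses need up to five uses per subject and ICC 0.2, and SAP 7.9.1.1 states no hypothesis, so no decision rule is affected. Both are true. They limit the consequence but do not make the interval valid for clustered uses. The subject counts and percentages in 7.9.1.3 do not repair it either, because they are given by MedDRA term and without an interval.

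**Conclusion.** The concern holds as a conditional one. The SAP names product uses as a possible primary unit and prescribes an interval that is not valid for several positively correlated uses per subject. With equal numbers of uses, the shortfall stays within about one point of 95% for two uses at ICC up to 0.2 or three uses at ICC up to 0.1. It reaches about 3 points for three uses at ICC 0.2 and about 7 points for five uses at ICC 0.2 (p = 20%, about 246 uses). Uneven numbers of uses do worse than equal numbers with the same mean. These sizes rest on assumed m and ICC and on the exact form of the interval. There is no problem with the subject as the unit, with one use per subject, or where an event is always attributed to a single use per subject. The text should be changed, but the consequence is limited to stated precision.

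**What to change.** In SAP 7.9.1.3, keep the binomial interval when the subject is the unit. When product uses are the unit and any subject contributes more than one, specify a two-sided 95% interval that accounts for clustering within subject and holds up with few events. One workable choice is the adjusted interval used above: Clopper-Pearson on the number of uses divided by the estimated design effect, floored at 1, with the plain exact interval when there are no events. Report the subject-level rate with its binomial 95% interval alongside. The AP, AD or SAP addendum should name the unit and say how an event is attributed to a use. If it sizes a study on uses, it should also multiply the 6.1 figure by an assumed design effect; for example, 245.86 × 1.4 = 344.2, so 345 uses in place of 246.

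The cost is one or two sentences and a short program, with no change to subject-level analyses or data collection. At p = 20% and about 246 uses, intervals widen by about 5% at m = 2, ICC 0.1, 19% at m = 3, ICC 0.2, and 35% at m = 5, ICC 0.2. They are also 2% to 4% wider when there is no clustering (m = 2 to 5). The repair is incomplete with very few subjects or events: at p = 5%, 24 subjects with three uses and ICC 0.2 give 94.0% against 92.8% plain, and 15 subjects with five uses and ICC 0.3 give 89.0% against 83.9%.
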